### **Sensitivity Analyses for PFS**

Three sensitivity analyses of PFS will be performed. All sensitivity analyses will be performed as described for the primary analysis of PFS. The sensitivity analyses are specified as follows:

1. The first sensitivity analysis will be conducted using the IRC response data as opposed to using investigator assessment of response.
2. The second sensitivity analysis will be conducted using the investigator response data where events of progression determined by CT scan will be included in the analysis.
3. The third sensitivity analysis will be conducted using sensitivity data generated by Perceptives where CT scan data is used to determine progression.

### **Subgroup Analyses for PFS**

Subgroup analyses will be conducted for PFS for the stratification factors provided subgroups are large enough to result in meaningful analyses. Figures displaying the survival curves will also be provided by treatment arms as well as for each of the stratification factors. The stratification factors include the following:

- 1) CR or PR at study entry
- 2) Number of previous induction treatments (2 vs 3)
- 3) Type of prior treatment: chemoimmunotherapy, only alkylating monotherapy, or other treatment

PFS will also be summarized by age group (<70, >=70), gender, race, baseline MRD status (negative, positive), and cytogenetics provided the subgroups are large enough to result in a meaningful analysis.

## **11.2. Secondary Efficacy Analyses**

### **Clinical Benefit:**

- Improvement in response

Improvement in response will be assessed by calculating the percentage of subjects who change from PR at baseline to CR during the study. Improvement in response will also be assessed by providing the frequency and percentage of subjects with negative and positive minimal residual disease (MRD). These rates will be compared between treatment groups with the Cochran-Mantel-Haenszel test adjusting for stratification factors (response at entry, number of prior treatments and type of prior treatment). The 95% confidence intervals will also be calculated for rates in each arm.

- Overall survival

Overall survival is defined as time (in months) from the randomization date to the date of death due to any cause. For subjects who do not die, time of death will be censored at the date of last contact. Survival distributions will be estimated using the Kaplan-Meier method, and survival curves will be compared using a stratified log-rank test. The same analysis will be conducted as described for the primary endpoint, PFS.

The analysis of overall survival will be performed when the second interim analysis for PFS takes place as well as at the end of the study. Subjects will be followed for 5 years after the 2 year treatment period.

- Time to next therapy

Time to next therapy is defined as the time (in months) from the randomization date to the date of receiving the next CLL treatment. For subjects who do not receive another CLL therapy, time of next therapy will be censored at the date of last contact. The same analysis will be conducted as described for the primary endpoint, PFS.

The analysis of time to next therapy will be performed when the second interim analysis for PFS takes place as well as at the end of the study.

- Progression-free survival after next-line therapy

This endpoint will be defined as the time (in months) from randomization until progression or death following next-line therapy and counting as events deaths prior to next-line therapy. Analysis of this endpoint will only include subjects who received next-line therapy and subjects who died prior to receiving next-line therapy. Subjects who receive next-line therapy and who do not have progression or death after next-line therapy will be censored at their last date of contact. If a subject dies prior to next-line therapy, this will count as an event. [REDACTED]

- Time to progression after next-line therapy

This endpoint will be defined as time (in months) from progression following randomization until progression or death following next-line therapy and counting as events deaths prior to next-line therapy. Analysis of this endpoint will only include subjects who received next-line therapy and who also had PD prior to receiving next-line therapy. Subjects with PD who died prior to receiving next-line therapy will also be included. Subjects who receive next-line therapy with a PD prior to receiving next line therapy and who do not have progression or death after next-line therapy will be censored at their last date of contact. If a subject dies prior to next-line therapy, this will count as an event. [REDACTED]

- Changes in patient reported outcome scores

Area under the curve (AUC) of change from baseline over time in the EORTC QLQ-C30, EORTC QLQ-CLL16 domain scores and total scores as well as the EQ-5D utility and VAS scores will be evaluated. Details of the methods used to evaluate changes in PRO domain and total scores will be provided in the Health Outcomes section of the RAP.

- Improvement of ECOG performance status

Improvement is defined as a decrease from baseline by at least one step on the ECOG performance status scale (improvement categorized as yes or no). The proportion of subjects with improvement will be compared between treatment groups with the Cochran-Mantel-Haenszel test adjusting for stratification factors (response at entry, number of prior treatments and type of prior treatment).

- B-symptoms/Constitutional symptoms

The proportion of subjects with no night sweats, no weight loss, no fever and no extreme fatigue will be summarized and compared to the proportion of subjects with at least one of the following: night sweats, weight loss, fever or extreme fatigue. The proportions will be compared between treatment groups with the Cochran-Mantel-Haenszel test adjusting for stratification factors (response at entry, number of prior treatments and type of prior treatment).

- Incidences of and number of subjects with grade 3 and 4 infections

The number and percentage of subjects with grade 3, 4 and 5 infections will be summarized by treatment group.

- Evaluation of myelosuppression (anemia, neutropenia, thrombocytopenia)

The number and percentage of subjects with myelosuppression will be summarized by treatment group.

- Frequency of transfusions

The number and percentage of subjects who receive blood transfusions during the study will be provided by treatment group.

- Incidence of Autoimmune Hemolytic Anemia (AIHA)

The number and percentage of subjects with autoimmune hemolytic anemia during the study will be provided by treatment group. The proportion of subjects with AIHA will be compared between treatment groups with the Cochran-Mantel-Haenszel test adjusting for stratification factors (response at entry, number of prior treatments and type of prior treatment).

- Human Anti-Human Antibodies (HAHA)

HAHA sample analysis will be conducted by a contract research organization using a validated assay. The number and percentage of subjects with positive and negative

HAHA results will be provided for each HAHA timepoint. A summary table with the overall HAHA assessment for each subject, considering ofatumumab concentration at the time of each HAHA sample collection, will be provided. A listing of HAHA results with the ofatumumab concentration at that time will be provided

- IgG, IgA, IgM

Summaries of IgG, IgA, and IgM will be provided at scheduled visits for actual values as well as for change from baseline.

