6.2.3. Minimal Residual Disease (MRD)

For subjects enrolling in the study who are in CR, baseline MRD will be assessed at screening, prior to any treatment visit.

For subjects who improve to a CR while on study, a bone marrow examination will be performed after at least 2 months of therapy or response while on study.

The bone marrow sample if available, and/or peripheral blood sample will be examined by flow cytometry with the following B-CLL MRD panel [Rawston, 2007]:

- CD5/CD19 with CD20/CD38
- CD5/CD19 with CD81/CD22
- CD5/CD19 with CD79b/CD43

In addition CD3/CD19 with CD14/CD45 analysis is performed to allow enumeration of CD19+ cells and contamination assessment and CD5/CD19 with Igλ/Igκ analysis is performed to confirm clonality.

Subjects with negative MRD will receive follow-up MRD assessments of the peripheral blood until MRD analysis becomes positive.

The absence of MRD is defined as less than one B-CLL cell per 10,000 leukocytes.

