Subgroup analyses will be conducted for PFS for the stratification factors.

Secondary Analyses

Clinical Benefit:

- Improvement in response

Improvement in response will be assessed by calculating the percentage of subjects who change from PR at baseline to CR during the study. Improvement in response will also be assessed by providing the frequency and percentage of subjects with positive minimal residual disease (MRD). These rates will be compared between treatment groups with the Cochran-Mantel-Haenszel test adjusting for stratification factors (response, number of prior treatments and type of prior treatment).

- Overall survival

Overall survival is defined as time from randomization to date of death. The same analysis will be conducted as described for the primary endpoint, PFS.

- Time to next therapy

Time to next therapy is defined as the time from randomization to date of receiving the next CLL treatment. The same analysis will be conducted as described for the primary endpoint.

- Progression-free survival after next-line therapy

This endpoint will be defined as time from randomization until progression or death following next-line therapy and counting as events deaths prior to next-line therapy. [REDACTED]

- Time to progression after next-line therapy

This endpoint will be defined as time from progression following randomization until progression or death following next-line therapy and counting as events deaths prior to next-line therapy. [REDACTED]

- Frequency of transfusions

The number and percentage of subjects who receive blood transfusions during the study will be provided.

- Evaluation of myelosuppression (anemia, neutropenia, thrombocytopenia)

The number and percentage of patients with myelosuppression will be provided.

- IgG, IgA, IgM

Summaries of IgG, IgA, and IgM will be provided at scheduled visits.

Disease Markers:

- Minimal Residual Disease (MRD)

The number and percentage of subjects with positive MRD will be provided. The proportion of subjects with positive MRD will be compared between treatment groups with the Cochran-Mantel-Haenszel test adjusting for stratification factors (response, number of prior treatments and type of prior treatment).

- B-cell monitoring

CD5/CD19 change from baseline will be summarized to assess the treatment effect. The number and percentage of subjects with complete B-cell depletion will be summarized.

- Prognostic markers correlating with clinical response

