11. APPENDICES

11.1. Appendix 1: Time and Events

Phase	SCREEN	Treatment or Observation (~ every 8 wks after 1 st visit)			Follow-up (every 3 months for 5 years)	WD
		1	2	3-14		
Visit	Screening	1	2	3-14	15-34	
Week	(-6 to -1)	1	2	9-97	109-337	
Month	0	1	1	3-25	28-85	
Visit Window		± 7d	± 3d	± 7d	± 14d	
Administration of Ofatumumab (if assigned to treatment group)		X	X	X		
Informed Consent	X					
Eligibility Criteria	X					
Demographics	X					
Medical History ¹	X					
Height	X					
Body weight	X		X	X	X	X
Physical Exam	X		X	X	X	X
Lymph node evaluation	X		X	X	X	X
Organ Evaluation	X		X	X	X	X
ECOG	X		X	X	X	X
ECG	X					
Adverse Event Assessments		X	X	X	X ¹²	X
Concomitant Medications		X	X	X	X ¹²	X
CT Scan	X			X ²	X ²	X
Bone marrow biopsy	X ³			X ³		
Flow cytometry (MRD)	X ³			X ³	X ³	X ³
Flow cytometry(CD5/CD19)	X			X	X ⁴	X
Prognostic Factors ⁵	X					X
Response Evaluation		X	X	X	X	X
PRO	X			X	X	X
Hematology ⁶	X	X	X	X	X	X
Biochemistry ⁶	X	X	X	X	X	X
Hepatitis ⁷ and Pregnancy Test	X					
Igs	X			X ^{8,9}		
HABA ¹⁰		X		X ^{8,9}	X ⁹	X
Coombs and CH50	X				X	
PK Sampling ¹¹		X	X	X	X	X
Vital Signs	X	X	X	X	X	

1. Medical history to include disease characteristics as defined in Section 6.1.
2. Screening, yearly while on study, at the subject's last treatment visit and upon relapse
3. For subjects in CR ONLY- may be confirmed with bone marrow biopsy/flow cytometry
4. Until B-cell value is within normal levels (See Section 6.3.1.2.)
5. Prognostic Factors as defined in Section 6.3.3
6. See Section 6.3.2
7. Subjects that are HBsAg negative, HBcAb positive and HBV DNA negative may be included but must undergo HBV DNA monitoring as listed in Section 6.3.4
8. At the subject's last treatment visit
9. Every six months. Igs may be assessed during infection per PI. (See Section 6.3.4)
10. HAHA for ofatumumab treatment only-predose, every six months, at last treatment, and 3& 6 months post last ofatumumab dose, regardless of when it occurs.
(See Section 6.3.4)
11. For pharmacokinetic sampling, see Table 5, Section 6.6; + 15 min window for 0.5h post EOI samples is allowed
12. Only SAEs and associated concomitant medications are to be reported from 60 days after the last dose/observation time. (See Section 6.4.8.)

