#### **Follow-up Phase:**

Survival and disease status assessments (physical examination and evaluation of peripheral blood samples) will be performed post treatment every 3 months for 5 years after last treatment.

Bone marrow examination is required for confirmation of CR at least 2 months post last treatment. MRD assessment will also be performed for subjects demonstrating CR. Subjects with negative MRD will receive follow-up MRD assessment of the peripheral blood until MRD becomes positive. CT-Scans are required for confirmation of CR and PR at least 2 months post last treatment.

Subjects demonstrating disease progression will be followed for survival status until study completion. Follow-up assessment after disease progression on treatment will assess survival status, date of next CLL therapy, type of therapy and response to therapy.

PRO measures (EORTC QLQ-C30, EORTC QLQ-CLL16, EQ-5D and a Health Change Questionnaire) will be administered for completion by the subject at follow-up visits.

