#### **Disease Markers:**

- Minimal Residual Disease (MRD)

The number and percentage of subjects with positive and negative MRD will be provided at each timepoint. The proportion of subjects with negative MRD and positive MRD will be compared between treatment groups with the Cochran-Mantel-Haenszel test adjusting for stratification factors (response at entry, number of prior treatments and type of prior treatment). An analysis of the time to first MRD positivity for subjects who were MRD negative at baseline will also be provided using Kaplan-Meier methodology.

- B-cell monitoring

The change and percent change of  $CD5^+CD19^+$  and  $CD5^-CD19^+$  from baseline will be summarized to assess the treatment effect, to monitor the normal B-cell population, and to follow their recovery. In addition, frequency and percentage of subjects with complete B-cell depletion and near-complete B-cell depletion will be summarized. Complete B-cell depletion is defined as the absolute value of  $CD5^+CD19^+$  and  $CD5^-CD19^+$  both equal to zero cells/uL. Near complete B-cell depletion is defined as the sum of the absolute value of  $CD5^+CD19^+$  and  $CD5^-CD19^+$   $<5$  cells/uL.

Tables that will be provided are:

- Summary of  $CD5^+CD19^+$  counts over time
- Summary of  $CD5^-CD19^+$  counts over time
- Summary of  $CD5^+CD19^+$  change from baseline (counts and percentage)
- Summary of  $CD5^+CD19^+$  percent change from baseline (counts and percentage)
- Summary of  $CD5^-CD19^+$  change from baseline (counts and percentage)
- Summary of  $CD5^-CD19^+$  percent change from baseline (counts and percentage)
- Summary of subjects with complete B-cell depletion Summary of subjects with near-complete B-cell depletion
- Prognostic markers correlating with clinical response

Cox-regression will be used to explore the relationship between PFS and the following explanatory variables: treatment group, cytogenetics (analyzed by FISH) at baseline,

IgVH mutational status at baseline,  $\beta$ 2 microglobulin at baseline, baseline CD20 and baseline complement level. Ctau and Cmax at Cycle 1 Day 1, Cycle 1 Day 8, and Cycle 4 and cytogenetics at relapse may also be considered as possible explanatory variables in the model.

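### MRD is measured only in subjects in CR, yet MRD rates are compared between arms as improvement in response with no rule for untested PR subjects, so the comparison can miss an improvement or read it as harm.

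*SAP*

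**What the plan says.** **Who is tested.** Protocol 6.2.3 covers two groups. At screening: "For subjects enrolling in the study who are in CR, baseline MRD will be assessed at screening". On study: "For subjects who improve to a CR while on study, a bone marrow examination will be performed", and the marrow sample and/or a blood sample is then examined for MRD. In protocol Appendix 1 the MRD row carries footnote 3: "For subjects in CR ONLY- may be confirmed with bone marrow biopsy/flow cytometry". SAP 3, Follow-up Phase, agrees: "MRD assessment will also be performed for subjects demonstrating CR". A subject who enters in PR and stays in PR has no planned MRD result.

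**What is compared.** Under improvement in response, SAP 11.2 gives two measures: the percentage changing from PR to CR, and then MRD: "Improvement in response will also be assessed by providing the frequency and percentage of subjects with negative and positive minimal residual disease (MRD"). Both are compared by CMH, adjusted for response at entry and for number and type of prior treatments. The Disease Markers part of SAP 11.2 repeats the MRD test: "The proportion of subjects with negative MRD and positive MRD will be compared between treatment groups". Protocol 8.3.5.1 names only the positive rate: "providing the frequency and percentage of subjects with positive minimal residual disease (MRD").

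**What is missing.** SAP 11 bases efficacy analyses on the ITT population unless otherwise specified. SAP 9.1 imputes no missing data, and its non-responder rule covers only subjects without any response data. SAP 12.7 and 12.8 give a denominator rule for safety percentages. There is no such rule for MRD.

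**The concern.** For a subject who enters in PR, having an MRD result depends on first reaching CR. That happens after randomisation and is something the drug may change. An MRD percentage is therefore not a plain measure of improved response, and its meaning depends on an unstated denominator.

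- **Tested subjects only.** Among PR entrants, the comparison asks whether MRD status differs between arms given CR. A gain in MRD-negative CR that comes through more CRs leaves that share unchanged.
- **All randomised subjects.** The MRD-negative rate then follows the improvement. The MRD-positive rate does not: a PR subject who improves to an MRD-positive CR moves from untested to positive, so improvement looks like harm. This is the only MRD rate the protocol names.

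At stake is a secondary efficacy result that could show nothing, or point the wrong way, beside a real gain in CR.

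**Working it through.** The documents give no CR rate, MRD rate or MRD power, so there is no plan figure to reproduce. All rates below are assumptions.

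**Inputs.** Evaluable subjects per arm: 478/2 = 239 (SAP 5.1). Assumed split: 190 in PR and 49 in CR at entry. CR entrants are 50% MRD-negative in both arms. Each PR entrant who reaches CR is tested once. The level is two-sided 0.05.

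**Model.** Among PR entrants, CR ~ Bin(190, c) and MRD-negative ~ Bin(CR, m), with c and m set per arm. The test is CMH over two strata h (PR and CR at entry):

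Z = Σ(a_h − n1_h·t_h/N_h) / √Σ[n1_h·n0_h·t_h·(N_h − t_h)/(N_h²(N_h − 1))]

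Here a_h is the ofatumumab count, n1_h and n0_h are the arm sizes, t_h is the total count and N_h = n1_h + n0_h. It rejects when |Z| > 1.96. The other stratification factors are left out.

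**Expected values among PR entrants (observation vs ofatumumab)**

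| Scenario | CR rate c | m given CR | CRs tested | MRD-neg of 190 | MRD-pos of 190 |
|---|---|---|---|---|---|
| A | 10% vs 25% | 50% vs 50% | 19 vs 47.5 | 9.5 (5.0%) vs 23.75 (12.5%) | 9.5 (5.0%) vs 23.75 (12.5%) |
| B | 10% vs 20% | 50% vs 25% | 19 vs 38 | 9.5 (5.0%) vs 9.5 (5.0%) | 9.5 (5.0%) vs 28.5 (15.0%) |
| C | 10% vs 20% | 50% vs 40% | 19 vs 38 | 9.5 (5.0%) vs 15.2 (8.0%) | 9.5 (5.0%) vs 22.8 (12.0%) |

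In A, MRD-negative CRs rise 2.5-fold while the tested-only share stays at 50% vs 50%. In C they rise by 60% while the tested-only share falls from 50% to 40%.

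**Simulated rejection, CR entrants included**

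| Test | A | B | C |
|---|---|---|---|
| Tested only, MRD-negative | 5% in total, evenly split | 18-19% against ofatumumab | 6% against ofatumumab |
| All randomised, MRD-negative | 48-49% for ofatumumab | 5% in total | 13% for ofatumumab |
| All randomised, MRD-positive | 48% higher on ofatumumab | 71% higher on ofatumumab | 44% higher on ofatumumab |
| PR-to-CR rate | 98% | 79% | 79% |

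Where two values are shown, repeat simulations differed by about a point. With c = 10% and m = 50% in both arms, every test rejects in about 5%.

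**Range for the split (170 PR + 69 CR to 210 PR + 29 CR per arm).** Scenario A, MRD-negative over all randomised: 37% to 63%. Scenario B, tested-only against ofatumumab: 13% to 27%. Scenario B, MRD-positive over all randomised: 56% to 84%. The directions do not change.

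**Different assumed rates.** With 80% in PR at entry, CR 5% vs 15% and negativity given CR 40% in both arms, tested-only rejection is again 5%. The MRD-positive rate over all randomised subjects is significantly higher on ofatumumab in 40% of trials (27% to 58% for a PR share of 70% to 90%).

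**The case against.** Four arguments on the other side carry weight.

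1. *The improvement is already tested.* The PR-to-CR percentage comes first in the same bullet, uses the same CMH test, and has 98% or 79% power above. This stands: a reader would see the higher CR rate beside the MRD result. It does not make the second measure sound, because that measure can contradict the first under one label.
2. *CR entrants are in the test.* Their CR status is a baseline feature, so selection on a post-randomisation outcome does not arise for them. This stands and reduces the effect. With PR entrants alone, scenario B would give 47% tested-only rejection and 92% for the MRD-positive rate, but that is not the planned test.
3. *ITT is the default population.* On that reading the MRD-negative rate is close to the right measure. This is a fair reading, but the SAP never says that untested subjects count as not negative, and the MRD-positive comparison remains.
4. *The consequence is small.* SAP 7 and 8.4 keep MRD outside the gatekeeping sequence, with p-values only nominal. The 280-event plan omits Tables 2.2070 and 2.2075. The final plan produces Table 2.2070 in an analysis declared descriptive. This stands and limits the weight of the point.

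A reader might infer that tested-only rejection in scenario B is an inflated type I error. The documents do not support that. They state no MRD null, and negativity given CR truly differs in that scenario (50% vs 25%), so rejection correctly answers a different question. Nor do they fix the tested-only denominator; it is one of two open readings.

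**Conclusion.** The point holds as a mismatch between the label and the comparison. The plan calls a between-arm comparison of MRD rates improvement in response, although MRD is known only given CR and no rule covers untested PR subjects. Counting tested subjects only, a gain that comes through more CRs is invisible (5% rejection against 48-49% in scenario A). Counting all randomised subjects, the MRD-positive rate rises with improvement (71% or 44% significantly higher on ofatumumab in scenarios B and C).

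The sizes rest on assumed CR and MRD rates and on an assumed entry split. Only the directions follow from the design. The reversal in the tested-only comparison needs negativity given CR to be lower on ofatumumab, and it is weak when the drop is modest (6% at 50% vs 40%).

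A reader might infer damage to the trial's main claim. There is none: PFS and the two inferential secondary endpoints do not use MRD.

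**What to change.** In SAP 11.2 (improvement in response and Disease Markers) and protocol 8.3.5.1:

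- Define the MRD improvement measure as MRD-negative CR on study among all randomised subjects in PR at entry. Count subjects not in CR, or not tested, as not MRD-negative.
- Test it by CMH stratified by number and type of prior treatments. Response at entry is then constant.
- Report CR-at-entry subjects separately by baseline MRD status, so that those already MRD-negative at screening are not counted as improved.
- Delete the between-arm test of the MRD-positive rate as a measure of improvement.
- Show MRD status among tested subjects descriptively, with the number tested in each arm.

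In scenario A this measure has 75% power (71% to 79% for 170 to 210 PR entrants per arm), and it rejects in 5% when the MRD-negative CR rate is equal in both arms. The cost is wording and a denominator change, using data already collected. The downside is that reported MRD-negative percentages become lower, because untested subjects count as not negative.
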